### 1.5.3. Final Analysis

After the primary analysis of both cohorts, the Sponsor will continue to follow the FD cohort for approximately 5 years after the first subject was enrolled in the cohort and may elect to discontinue follow-up of specific treatment arms of MRD cohort. Subjects who are continuing ibrutinib at the time of study arm closure may be offered a separate extension study to continue ibrutinib. When the study closes, a final analysis will be performed for both cohorts, and a CSR addendum will be prepared.

## 1.6. Testing Procedure and Level of Significance

For both cohorts, hypothesis testing will be performed independently (without multiplicity adjustment) for the primary endpoint only. Other endpoints will be summarized descriptively with 95% confidence interval (CI) whenever applicable.

- Primary endpoint for MRD cohort, 1-year DFS rate in MRD-negative randomized subjects, will be tested between placebo and ibrutinib arms at a 2-sided alpha level of 0.05.
- Primary endpoint for FD cohort, CRR, will be tested in non-del 17 subjects at a 1-sided alpha level of 0.025.

## 1.7. Blinding and Randomization Methods

### 1.7.1. Blinding Method

The FD cohort and Pre-Randomization phase of MRD cohort are an open label single arm study design.

MRD cohort subjects who achieve confirmed MRD negativity after completing the 12 cycle Ibr + Ven treatment will be randomized and treated in a double blind manner. Subjects, investigator and sponsor's study staffs are all blinded to treatment assignment until subject experiences a confirmed MRD-positive relapse or PD event and plans to reintroduce treatment as per protocol. At such time, the specific subject and their treating investigator may request unblinding as needed to make subsequent treatment decisions. The sponsor's independent clinician verifies the DFS event criteria have been met per protocol and approves unblinding on the Interactive Response Technology (IRT) system. Details are described in the Minimizing Bias Document.

MRD cohort subjects who do not achieve confirmed MRD negativity after completing the 12 cycle Ibr + Ven treatment are to be randomized in an open label manner. Neither the subjects nor the investigators are blinded to treatment. However, no aggregated data summary by arm is allowed until data are extracted and approved for the primary analysis for MRD cohort.

In addition to investigator assessment, IRC will evaluate the responses for both cohorts independently. Members of the IRC are blinded to the study treatment for all subjects. The IRC data flow and workflow are detailed in the IRC charter.

### **1.7.2. Randomization Method**

After completing the 12 cycle Ibr + Ven treatment in MRD cohort, subjects will be randomized centrally by two separate schemes according to MRD status, each stratified by IGHV status (Unmutated vs mutated [including borderline or not evaluable]):

- Subjects who achieve confirmed MRD negativity are to be randomized to receive double blind study treatment, either placebo or ibrutinib.
- Subjects who do not achieve confirmed MRD negativity are to be randomized to receive open label treatment, either single agent ibrutinib or Ibr + Ven.

In each scheme, subjects will be randomized in a 1:1 ratio within each randomization stratum. This randomization scheme will be implemented within the IRT system.

## 2. GENERAL ANALYSIS CONSIDERATION

### 2.1. Analysis Sets

**All treated population** includes all enrolled subjects who received at least 1 dose of study drug (ibrutinib or venetoclax or both). All analysis including baseline, disposition, efficacy and safety analysis will be based on this population.

**MRD-negative randomized population:** defined as all treated subjects in the MRD Cohort who are randomized to the double blind ibrutinib or placebo arms. Subjects in this population will be analyzed according to the treatment to which they are randomized.

**MRD-positive randomized population:** defined as all treated subjects in the MRD Cohort who are randomized to the open label ibrutinib or Ibr + Ven arms. Subjects in this population will be analyzed according to the treatment to which they are randomized.

**Non-del 17p population** includes subjects of all treated population without del 17p abnormality according to non-missing baseline FISH results. The primary analysis of the primary and main secondary endpoints for FD cohort will be based on this population.

### 2.2. Definition of Subgroups

Subgroup analyses will be performed for the selected variables (Table 1) to assess the internal consistency of the treatment benefit. The subgroup variables and the cutoff values may be further modified if warranted.

**Table 1: Baseline Subgroups**

Baseline Characteristics	Subgroups	Analysis Type
Age	<65 years, ≥65 years	• CRR
Gender	Male, Female	• MRD negativity rate
Race	White, Non-White	• Adverse Event
ECOG score	0, 1-2	• CRR • MRD negativity rate
Rai stage	Stage 0-II, III-IV	
Bulky disease	LDi <5 cm, ≥5 cm	
Del 17p	Yes, No	
Del 17p or TP53 mutated	Yes, No	
FISH*	Del 17p, Del 11q, Others	
IGHV per central lab	unmutated, mutated	
Creatinine clearance	<60 mL/min, ≥60 mL/min	• Adverse Event
NCI ODWG Liver Function Classification	Normal, Abnormal	

ECOG = Eastern Cooperative Oncology Group, FISH = Fluorescence in Situ Hybridization,  
NCI ODWG= National Cancer Institute Organ Dysfunction Working Group

\*Classified in 3 categories per hierarchical order (Dohner et al,2000): del 17p, del 11q without del 17p, and all others (neither del 17p nor del 11q identified).

### **3. SUBJECT INFORMATION**

Subject information will be summarized descriptively. No inferential tests will be performed.

#### **3.1. Subject Disposition**

Subject enrollment will be summarized by region, country, site and by cohort. Subject randomization in MRD cohort will be summarized by arm and by stratification factors. Subject disposition for each study treatment and for study participation will be tabulated. The overall duration of receiving any study treatment and time on study will be summarized correspondingly.

Time on study is defined in the same way as overall survival with reversed censoring, i.e. subjects who died will be censored at death date. The Kaplan-Meier method will be used to estimate the median time on study.

#### **3.2. Demographics and Baseline Characteristics**

Demographic information and baseline characteristics including but not limited to age, gender, race, histology type, time from initial diagnosis, staging, and potential prognostic factors will be summarized with descriptive statistics.

#### **3.3. Prior and Concomitant Medications**

Medications will be coded to preferred term and Anatomical Therapeutic Chemical (ATC) class according to World Health Organization (WHO) Drug dictionary.

Prior medications are defined as medications that started prior to the first dose date of study drug. Concomitant medications are defined as medications that were taken at any time on treatment (i.e. from the date of the first dose of study drug through the date of the last dose of study drug).

Concomitant medications will be summarized by therapeutic class and preferred term in the all treated population. The following concomitant medications of special interest will be summarized separately: growth factors, blood supportive products and immunoglobulin, CYP3A inhibitors/inducers, anticoagulants and/or antiplatelet.

#### **3.4. Extent of Exposure to Study Treatment**

Exposure to ibrutinib and venetoclax will be summarized separately for treatment duration and dosing information (e.g. total cumulative dose administered, relative dose intensity, ibrutinib or venetoclax dose reduction due to adverse events).

#### **3.5. Subsequent Antineoplastic Therapies**

Subsequent CLL/SLL antineoplastic agents will be summarized by type of therapies.

#### 4. ANALYSIS FOR ENDPOINTS

All endpoints will be analyzed in both MRD and FD cohorts separately and pooled except DFS for MRD cohort only. The definition and analysis methods are the same for both cohorts on the same endpoint with some variations on analysis population and analysis period in terms of primary analysis vs supportive analysis of the endpoint.

In general, the analysis population for the primary analysis is the all treated population for the MRD cohort and the non-del17p population for FD cohort. All analyses for the FD cohort will be repeated on the all treated population as supportive analyses.

Unless otherwise specified, the analysis period for primary analysis of endpoints is from the first dose date of study treatment to the first dose date of subsequent antineoplastic therapy or reintroduction of study treatment, whichever occurs earlier, unless otherwise specified. For MRD cohort, this is the overall period including pre-randomization phase and randomization phase. All by-arm summaries of the MRD cohort are also based on the overall period except DFS analyzed within randomization phase only. Summaries for CRR, ORR, MRD negativity rate within the pre-randomization phase (first 16 cycles) in the all treated population of MRD cohort will be provided as supportive analyses.

Table 2 summarizes the efficacy endpoints and analysis methods to be performed. For subgroup and exploratory or supportive analyses, only those providing meaningful information will be presented.

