10.4.6. Progression-Free Survival (PFS)

Progression-free survival (PFS) is defined as the time from the first dose date of study treatment until disease progression (per IWCLL 2008 criteria) or death from any cause, whichever occurs first.

In the MRD cohort and the Fixed Duration cohort, PFS is a secondary endpoint and will be analyzed in the all treated population. Distribution of PFS will be estimated using Kaplan-Meier method. Median PFS, landmark estimates, and their corresponding 95% CI will be provided.

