Complete response rate (CRR)	The proportion of subjects achieving a best overall response of CR or CRi on or prior to initiation of subsequent antineoplastic therapy or, if applicable, reintroduction of study treatment, whichever occurs earlier.	
Primary The point estimate of CRR per investigator assessment and the corresponding 95% CI based on normal approximation to the binomial distribution will be provided. In FD cohort non-del17p population, p value for testing <math>CRR \leq 37\%</math> vs <math>CRR > 37\%</math> using asymptotic test for the binomial proportion will be calculated.
 
Sensitivity CRR per IRC assessment.
 
Supportive 1. Duration of complete response (DOCR defined as the interval between the date of initial CR or CRi until disease progression or death from any cause, whichever occurs first.) for subjects who achieved CR or CRi. 2. Durable CRR (defined as proportion of subjects with DOCR <math>\geq</math> 336 days (12 cycles))
 
Subgroup (defined in table 1) The point estimate of CRR per investigator assessment and its 95% CI by normal approximation to the binomial distribution for each subgroup.

Secondary Endpoints for MRD and FD Cohorts		
Overall response rate (ORR)	The proportion of subjects achieving a best overall response of CR, CRi, nPR, or PR on or prior to initiation of subsequent antineoplastic therapy or, if applicable, reintroduction of study treatment, whichever occurs earlier.	
Primary The point estimate of ORR per investigator assessment and the corresponding 95% CI based on normal approximation to the binomial distribution will be provided.
 
Sensitivity ORR per IRC assessment.

Duration of response (DOR)	Duration of response will be calculated for the subjects achieving a response (CR, CRi, nPR, PR) per investigator assessment and is defined as time from the date of initial response including PR with lymphocytosis to the date of disease progression or the date of death from any cause, whichever occurs first. For subjects without documented PD or death, DOR was censored at the date of last adequate disease assessment.	
Primary Kaplan-Meier estimates of median DOR time per investigator assessment and landmark estimates with 2-sided 95% CIs.
 
Sensitivity DOR per IRC assessment

Endpoint	Definition	Analysis Method

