MRD negativity rate	The proportion of subjects achieving MRD negativity which is defined as <1 CLL cell per 10,000 leukocytes (<1 x 10  ) as assessed by flow cytometry of a peripheral blood (PB) or bone marrow (BM) aspirate sample per central laboratory on or prior to initiation of subsequent antineoplastic therapy or, if applicable, reintroduction of study treatment, whichever occurs earlier.	
Primary The point estimate of MRD negativity rate and the corresponding 95% CI based on normal approximation to the binomial distribution will be provided.
 
Sensitivity MRD negativity rate by sample type (PB or BM)
 
Supportive MRD negativity rate by best overall response categories (CR/CRi, nPR/PR/PRL, and all others including non-responders and those off study without response assessment).

Tumor Lysis Syndrome (TLS) risk reduction	The reduction of the proportion of subjects who are at high risk of TLS after the ibrutinib lead-in compared with baseline.	
Primary The point estimate of the difference in proportions of subjects with high risk of TLS (at baseline - after ibrutinib lead in) and the corresponding 95% CI (adjusting correlation of paired data) will be provided.
 
Supportive Reduction of the proportion of subjects with hospitalization indicated due to tumor lysis Syndrome (TLS) risk (i.e. subjects with high TLS risk and subjects with medium risk of TLS and creatinine clearance <80 mL/min).

Progression Free Survival (PFS)	
Time from the date of first study treatment to the date of disease progression per investigator assessment or date of death from any cause, whichever occurs first, regardless of the use of subsequent antineoplastic therapy prior to documented PD or death.
 
For subjects without documented PD or death, PFS will be censored at the date of last adequate disease assessment. For subjects without adequate disease assessment post-baseline, PFS will be censored on the date of first study treatment.
	PFS distribution will be estimated by Kaplan-Meier method: median PFS and landmark estimates with 2-sided 95% CIs will be provided.

Overall Survival (OS)	Time from the date of first study treatment to the date of death from any cause. For subjects who are not known to have died at the time of the analysis, OS will be censored at the date of last known alive.	Kaplan-Meier estimates of median OS time and landmark estimates with 2-sided 95% CIs.

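### The SAP does not settle whether PFS, DOR and duration of complete response stop at reintroduction of study drug; its default would censor MRD-negative subjects restarted for MRD relapse before progression, unlike the protocol definitions.

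*SAP*

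**What the plan says.** SAP section 4 sets a default analysis period running from first dose to the "first dose date of subsequent antineoplastic therapy or reintroduction of study treatment, whichever occurs earlier", subject to an exception for anything specified otherwise. For the MRD cohort it adds: "All by-arm summaries of the MRD cohort are also based on the overall period except DFS analyzed within randomization phase only".

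Table 2 of the SAP then treats the endpoints differently:

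- **CRR, ORR and MRD negativity** carry the cut-off in the row itself: "on or prior to initiation of subsequent antineoplastic therapy or, if applicable, reintroduction of study treatment, whichever occurs earlier".
- **PFS** runs from first dose to progression or death "regardless of the use of subsequent antineoplastic therapy prior to documented PD or death". Reintroduction is not named. The censoring rule is: "For subjects without documented PD or death, PFS will be censored at the date of last adequate disease assessment".
- **DOR** names neither stop. Its censoring rule is: "For subjects without documented PD or death, DOR was censored at the date of last adequate disease assessment".
- **DOCR**, in the supportive analyses for CRR, runs to progression or death and names neither stop.

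Protocol 10.4.6 defines PFS from the "first dose date of study treatment until disease progression (per IWCLL 2008 criteria) or death from any cause", with no stop at reintroduction. Protocol 10.4.5 treats DOR the same way. SAP section 6 lists one change from the protocol, a change of terminology.

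Protocol 3.1.2 allows reintroduction in the MRD-negative arms after confirmed MRD-positive relapse, progression, or both. In the MRD-positive ibrutinib arm and in the Fixed Duration cohort (Protocol 3.1.3), it follows confirmed progression.

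**The concern.** The SAP lists subsequent antineoplastic therapy and reintroduction as two separate stops. When the PFS row lifts one by name and is silent on the other, a programmer can defensibly leave the second in force. For DOR and DOCR the literal reading leaves both in force.

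In the MRD-negative arms, a restart without progression is triggered by MRD-positive relapse: CLL cells at or above 1 in 100 leukocytes, confirmed twice, after being below 1 in 10,000 (Protocol 7.2.1.4). Censoring at that restart would remove subjects because of a change in their disease, so the censoring would be informative. It would also be unequal: SAP section 1.4 assumes a 1-year disease-free rate of 60% on placebo and 30 points more on ibrutinib. At stake is what the by-arm PFS and DOR displays mean, in a cohort that asks whether ibrutinib can be stopped.

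**Working it through.** The plan states no figure on this point, so there is none to reproduce. The check has two parts.

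**Does the text decide the matter?**

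- For a stop: the default covers by-arm summaries. If a row's own censoring rule were enough to displace it, the extra clause in the PFS row would be redundant.
- Against a stop: the default yields to other specification. The PFS and DOR rows censor only subjects without progression or death, and do so at the last adequate assessment. The rows meant to stop at reintroduction say so.
- Protocol 3.1.2 provides a new baseline and a time to next progression only for subjects who had progressed before reintroduction. After an MRD-triggered restart, a later progression is therefore the first one and belongs in PFS as the protocol defines it.

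Both readings can be defended, so the rule is undefined.

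**What would a stop do? First illustration: constant hazards.** All relapsers restart at once. Inputs:

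- Total DFS hazard a = -ln(0.60) = 0.5108 per year on placebo and -ln(0.90) = 0.1054 on ibrutinib (rates from SAP 1.4).
- h0 = 0.02 per year, progression or death without MRD relapse (assumed, same in both arms).
- h1 = 0.07 per year after restart (assumed). As an anchor, Protocol 1.4 and 1.1.2 cite 18-month PFS of 90% and 89% on first-line single-agent ibrutinib: -ln(0.90)/1.5 = 0.070 and -ln(0.89)/1.5 = 0.078.
- Relapse hazard λ = a - h0 = 0.4908 on placebo and 0.0854 on ibrutinib.

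Stopped at restart: S(t) = exp(-h0·t).

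Followed through: S(t) = exp(-a·t) + λ[exp(-h1·t) - exp(-a·t)]/(a - h1).

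At t = 3 years from randomization:

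- Stopped, both arms: exp(-0.06) = 0.942.
- Followed, placebo: 0.2160 + 0.4908 × (0.8106 - 0.2160)/0.4408 = 0.878.
- Followed, ibrutinib: 0.7290 + 0.0854 × (0.8106 - 0.7290)/0.0354 = 0.926.

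| Arm, years from randomization | Stopped | Followed through | Difference (points) |
|---|---|---|---|
| Placebo, 1 | 98.0% | 97.0% | +1.0 |
| Placebo, 2 | 96.1% | 92.7% | +3.4 |
| Placebo, 3 | 94.2% | 87.8% | +6.4 |
| Ibrutinib, 3 | 94.2% | 92.6% | +1.6 |

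Here stopping hides an arm difference of 92.6 - 87.8 = 4.8 points. The sign is positive only if h1 exceeds h0. Over h0 from 0.01 to 0.05 and h1 from 0 to 0.30, the 3-year difference runs from -6.3 to +30.2 points on placebo and from -1.1 to +8.3 on ibrutinib.

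The SAP measures PFS from first dose, and randomized treatment starts after 16 × 28 = 448 days. Three years from first dose is therefore 3 - 448/365.25 = 1.77 years from randomization. The same formulas then give 96.5% against 93.8% on placebo, a difference of about 2.8 points.

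**Second illustration: progression only after MRD relapse (simulation).** Assumptions: exponential time to relapse with 1-year DFS of 60-90%; median relapse-to-progression of 1-2 years untreated; 50-90% restart 3 months after relapse; progression hazard after restart 0.05-0.15 per year. At 3 years from randomization, stopping differs from following through by about -7 to +7 points. In the scenario with 60% DFS, a 1-year median and 90% restarting:

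- 3 years from randomization: 73.9% stopped against 71.2-79.1% followed through, a difference of -5.2 to +2.7 points.
- 3 years from first dose: 85.6% stopped, a difference of about -1.6 to +1.5 points.

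**The case against.** The best case on the other side is that each row's own rule governs. The OS row has no clause lifting either stop, yet nobody would end OS at new therapy, because the row censors at the date last known alive. By the same logic, PFS and DOR run to progression or death, in line with the protocol. This stands as a possible reading, and it is why the SAP cannot be said to stop PFS as a settled rule. It does not close the gap, because the PFS row shows the author thought an explicit override was needed for one of the two stops.

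A reader might also infer that by-arm PFS will be too high and will understate the cost of stopping ibrutinib. The documents do not support that. The sign depends on hazards they do not give, and effective reintroduced therapy could remove or reverse it. A much larger figure comes from comparing the stopped curve with PFS had nobody restarted: in the scenario above, 73.9% against 47.1% at 3 years from randomization. On the SAP's first-dose clock that gap is 85.6 - 71.7 = 13.9 points. Either way, the comparator is a hypothetical that the protocol definition does not estimate.

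Materiality is limited. Reintroduction is optional, needs Medical Monitor approval and may be delayed until treatment is indicated (Protocol 8.4). Subjects restarted for progression already have their event.

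**Conclusion.** The concern holds as a gap and a conflict between documents. The SAP's default, applied literally, would censor DOR and DOCR, and arguably PFS, at an MRD-triggered restart. The protocol definitions of PFS and DOR do not, and SAP section 6 declares no departure.

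Such censoring would be informative and, on the plan's own disease-free rates, more frequent on placebo. Its direction and size remain open. The illustrations run from negligible to several points, and further at extreme hazards; all rest on assumed hazards, restart uptake and timing.

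The effect is confined to the MRD-negative arms and to summaries that include them. The primary DFS test is unaffected because MRD-positive relapse is itself a DFS event. PFS and DOR are descriptive under SAP section 1.6. The point is worth correcting because the rule is ambiguous for named secondary endpoints and the remedy is nearly free.

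**What to change.** In SAP Table 2, state for PFS, DOR and DOCR that the first progression and death count as events regardless of subsequent antineoplastic therapy and regardless of reintroduction of study treatment. This agrees with Protocol 10.4.5 and 10.4.6. Report censoring at reintroduction as a labelled sensitivity analysis. If the sponsor prefers censoring as the main rule, SAP section 6 should declare it as a change from the protocol.

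The cost is a phrase in the PFS and DOR rows and in the DOCR definition, plus one sensitivity analysis. No new data are needed: response assessment and CT after reintroduction are already scheduled (Protocol 8.4, Appendices C and D). The main estimate will then include the effect of reintroduced therapy, and the table footnotes should say so.

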MRD-negative remission is associated with superior PFS and OS with chemoimmunotherapy (CIT) in patients with CLL (Thompson 2016), however whether confirmed MRD-negative remissions with novel non-CIT regimens will also translate into a survival benefit is not yet known. Additionally, it will be important to understand if extended treatment with ibrutinib in patients without confirmed MRD negative remissions after 15 cycles can lead to deeper responses and attainment of MRD-negativity. This Phase 2 placebo-controlled study will investigate the activity of ibrutinib plus venetoclax in treatment-naive CLL subjects by assessing the ability to achieve complete clinical response, MRD-negative response, and the durability of response in the setting of ibrutinib discontinuation.

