3.1.2. MRD Cohort: Randomization Phase (Including Re-introduction Period)

Eligible subjects will be randomized in a 1:1 ratio based on their MRD status (see below). Subjects will be stratified by immunoglobulin heavy-chain variable region (IGHV) status in each randomization strata.

Randomization Phase - MRD-negative subjects (Double-blind):

Eligible subjects who achieve a confirmed MRD-negative response will be randomized to receive blinded treatment of ibrutinib (venetoclax discontinued) vs placebo (ibrutinib and venetoclax discontinued). The randomization will be stratified by IGHV status. Subjects will be assessed for disease-free survival as measured by continued MRD-negative response without progression or death at least 1 year after randomization. MRD status will be evaluated every 3 cycles in PB. MRD should also be reassessed in BM aspirate after an additional 12 cycles.

Randomization Phase - MRD-positive subjects (Open-label):

Those subjects who do not achieve a confirmed MRD-negative response (MRD-positive) after 12 cycles of the combination will be randomized to receive open label treatment of I+V vs ibrutinib alone (venetoclax discontinued). The randomization will be stratified by immunoglobulin heavy-chain variable region (IGHV) status. Subjects will subsequently be assessed for MRD-negative response. MRD status will be evaluated every 3 cycles in peripheral blood. MRD should also be reassessed in BM aspirate after an additional 12 cycles and at any time in subjects who become MRD negative in PB. For subjects receiving I+V, venetoclax can be administered for up to approximately 2 years per treatment course, until PD or unacceptable toxicity, or until this arm's study closure, whichever is earlier. Subjects who are continuing on

ibrutinib at time of study arm closure may be offered a separate extension study to continue ibrutinib.

Reintroduction of therapy:

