7.2.1.4.1. MRD-Negativity

MRD-negativity is defined as <1 CLL cell per 10,000 leukocytes ($<1 \times 10^{-4}$), as assessed by flow cytometry of a peripheral blood (PB) or bone marrow (BM) aspirate sample.

Confirmed MRD-negative response for randomization purposes requires MRD-negativity serially over at least 3 cycles, with negativity in both BM and PB. Subjects who do not achieve confirmed MRD-negative status are not considered to have a MRD-negative response for randomization purposes in the MRD cohort. See [Section 7.1.3.3](#) for MRD assessment schedule.

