Exploratory Endpoints for MRD and FD Cohorts		
		

[1] MRD-positive relapse is defined as an increase in CLL cells <math>\geq 1</math> per 100 leukocytes (<math>\geq 1 \times 10^{-2}</math>) confirmed on two consecutive occasions, after achieving MRD negativity, as assessed by flow cytometry of a PB or BM aspirate sample.
 
[2] MRD samples tested within 5 days after collection are considered valid and can be used in DFS analysis.
 
[3] Adequate disease assessment is defined as physical examination and CBC, or CBC and CT scan within 56 days of each other.
		

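### The SAP drops the protocol's randomisation-phase safety window for the MRD cohort; by-arm MRD negativity in the MRD-positive arms is also cumulative from first dose

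*SAP*

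**What the plan says.** **Safety.** Protocol 10.4.11 gives the MRD cohort two analyses: the all-treated population before randomisation, and a safety population during the randomisation phase. A summary across both phases is optional. SAP section 5 plans treatment-emergent adverse events (TEAEs) for the first 16 cycles and for the whole treatment-emergent period, in the all-treated population. It names no randomisation-phase window. The safety population is defined in neither protocol 10.1 nor SAP 2.1. SAP section 6 lists a single change from the protocol, a change of terminology.

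**Efficacy.** SAP section 4 states: "All by-arm summaries of the MRD cohort are also based on the overall period except DFS analyzed within randomization phase only". The only phase-specific efficacy summaries it describes are those "within the pre-randomization phase (first 16 cycles) in the all treated population of MRD cohort will be provided as supportive analyses", so they are not split by arm. SAP Table 2 counts MRD negativity from any sample "assessed by flow cytometry of a peripheral blood (PB) or bone marrow (BM) aspirate sample per central laboratory", and complete response as "The proportion of subjects achieving a best overall response of CR or CRi on or prior to initiation of subsequent antineoplastic therapy". Both are ever-achieved proportions.

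Entry to the two randomisations uses a stricter rule, in protocol 7.2.1.4.1: "Confirmed MRD-negative response for randomization purposes requires MRD-negativity serially over at least 3 cycles, with negativity in both BM and PB". Subjects who fail it go to the MRD-positive randomisation: ibrutinib plus venetoclax (I+V) or ibrutinib alone. For them protocol 3.1.2 says "Subjects will subsequently be assessed for MRD-negative response". Protocol 1.4 wants to learn whether extended ibrutinib in patients without confirmed negativity after 15 cycles "can lead to deeper responses and attainment of MRD-negativity".

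**The concern.** In the MRD-negative stratum the trial asks whether ibrutinib can be stopped. Toxicity on double-blind ibrutinib versus placebo is half of that question. Toxicity of I+V versus ibrutinib alone is the matching question in the other stratum. An overall-period table charges the placebo arm with events from 16 cycles of active treatment. Because each subject counts once per event, the shared history pulls the arms together. The protocol foresaw a separate window and the SAP does not carry it over.

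The efficacy issue has the same mechanism and lower stakes. A subject who was negative in blood once before Cycle 17, but never confirmed in both compartments, is already a success in whichever MRD-positive arm they enter. DFS does not apply to those arms. The pre-randomisation summary is not by arm, so new conversions cannot be recovered by subtraction.

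**Working it through.** **1. Safety windows side by side**

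| Window | Protocol 10.4.11 | SAP section 5 |
|---|---|---|
| Pre-randomisation | planned | planned (first 16 cycles) |
| Randomisation phase | planned | absent |
| Overall | optional | planned |

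Randomised treatment starts on Cycle 17 Day 1 (SAP 1.1). For a subject who completes 12 randomised cycles, 16/(16+12) = 57% of the observed cycles are shared. Of those 16, 13 (Cycles 4 to 16) are scheduled with venetoclax.

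The protocol counts subjects with at least one occurrence. Let r be the share in each arm with a given event before Cycle 17, and p the new-onset rate afterwards among the rest. The overall table shows r + (1-r)p. With p assumed at 30% vs 10%:

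- r = 30%: 51% vs 37%, a difference of 14 points
- r = 60%: 72% vs 64%, 8 points
- r = 90%: 93% vs 91%, 2 points

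The true difference is 20 points each time. Section 5 does not say whether the first-16-cycle table is split by eventual arm. If it were, subtraction would give first occurrences only, and recurrences after randomisation would be lost.

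**2. Efficacy: the plan's own figures first**

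SAP 1.5.1 reports early MRD rates with exact intervals. Both reproduce:

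- blood-negative after 9 cycles: 23/30 = 76.7% (57.7% to 90.1%)
- confirmed negative: 11/14 = 78.6% (49.2% to 95.3%)

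**Dilution.** Let f be the share of an MRD-positive arm with any negative sample before randomisation, and p1, p2 the later conversion rates among the rest. The cumulative difference is

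[f + (1-f)p1] - [f + (1-f)p2] = (1-f)(p1 - p2).

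**Lower bound on f.** The documents do not give f. Let c be the confirmed-negative rate. At most c of all subjects are both confirmed and early blood-negative, so at least 0.767 - c are early blood-negative but not confirmed. Hence f >= (0.767 - c)/(1 - c). For an assumed true difference of 20 points:

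| c | Lower bound on f | 20 points shows as at most |
|---|---|---|
| 40% (planned, SAP 1.4) | 0.367/0.60 = 61% | 8 |
| 49% (lower limit observed) | 0.277/0.51 = 54% | 9 |
| 60% | 0.167/0.40 = 42% | 12 |
| 70% | 0.067/0.30 = 22% | 16 |
| 79% (observed 11/14) | 0 | 20 |

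At c = 40% with the lower limit of 58% for the blood rate, the bound is (0.58-0.40)/0.60 = 30%, or at most 14 points.

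**Precision of a post-randomisation table.** For an assumed 40% vs 20%, the 95% half-width is 1.96 x sqrt((0.24+0.16)/n). Arm size is 150 x 0.60/2 = 45 at the planned rate, or 150 x (3/14)/2 = 16 at the observed rate. The half-widths are 18 and 31 points. If only half of each arm is still at risk of new conversion (about 22 or 8 subjects), they are 26 and 44 points.

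**The case against.** On safety, the best defence is that protocol section 10 leaves specifics to the SAP, that the SAP keeps the pre-randomisation summary and makes the optional overall one firm, and that the protocol's own safety population is undefined. All of that is true. It makes this an omission, not a wholesale reversal. It does not supply the missing window, and no redaction touches these passages.

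On efficacy the defence is stronger.

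- A reader might infer that no analysis of conversion after randomisation exists. The documents do not support that. The exploratory objectives and endpoints are redacted (protocol 2.3 and 10.2, SAP 1.2 and Table 2), as is an exploratory item in protocol 10.4.1, so such an analysis may be there. The visible sentence in SAP section 4 excepts only DFS.
- A reader might infer a breach of the protocol. Protocol 10.4.1 itself bases MRD negativity on the all-treated population, and no visible endpoint is by-arm conversion. The gap is against the design aim only.
- SAP Table 2 plans a split by blood and marrow. Marrow MRD is scheduled only from Cycle 16 (protocol Table 11), apart from marrows taken to confirm CR, so it carries less early history. It is still cumulative and helps only partly.
- A reader might take f >= 61% as the size of the problem. It needs the planned 40% confirmed rate, which lies outside the observed interval of 49% to 95%. At the observed rate the bound is 0.
- A reader might call the MRD-negative arms' table a defect, since it is about 100% vs 100% by entry criterion. It is uninformative, but DFS covers loss of negativity in those arms. The relapse threshold of 1 CLL cell per 100 leukocytes, "confirmed on two consecutive occasions, after achieving MRD negativity", is the one the protocol sets in 7.2.1.4.2.

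**Conclusion.** The safety point stands and is the main one. The protocol plans a randomisation-phase safety analysis, the SAP has none, and SAP section 6 does not say so. By-arm adverse event tables on the planned windows would not isolate toxicity on randomised treatment. At 12 randomised cycles, 57% of observed cycles are shared. The 14, 8 and 2 point figures rest on assumed event rates.

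The efficacy point stands in a narrower form, for the MRD-positive arms only and as a descriptive matter. The cumulative table shrinks a true conversion difference by the factor 1-f. The lower bound on f runs from 0 to 61% depending on c, and f itself may be higher than its bound. The calculation assumes that the first 30 subjects represent the cohort and, for the arm sizes, that every subject without confirmed negativity is randomised. Protocol 3.1.1 excludes some, so 45 and 16 per arm are upper limits. Randomisation balances f in expectation, so the dilution favours neither arm.

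The primary DFS test is unaffected, and all other endpoints are descriptive (SAP 1.6).

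**What to change.** **Safety (SAP 2.1 and 5).** Define the randomisation-phase safety population as randomised subjects with at least one dose of randomised treatment. Add by-arm TEAEs with onset or worsening on or after the first randomised dose, in both randomisations. Keep the overall tables and label them cumulative.

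**Efficacy (SAP 4, MRD-positive arms).** Add one descriptive by-arm table from post-randomisation samples: blood at Cycles 20, 23, 26 and 29, and marrow at Cycle 29 where sampled. Show MRD status for all randomised subjects, and new negativity among those not negative in that compartment at their last pre-randomisation sample. Give the numbers missing, because protocol Table 11 can waive the Cycle 29 aspirate after an earlier negative marrow. State that the estimates will be imprecise. If a redacted exploratory endpoint already does this, a cross-reference is enough.

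**Cost.** SAP wording and a few tables from assessments already scheduled. Alpha, sample size, treatment and the DFS test do not change. The drawbacks are wide intervals in the MRD-positive arms and marrow data that may not be missing at random.
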